All participants will be assigned a unique participant identification number (PIN). These PINs will be used to identify participants on research materials, surveys, transcripts, ACASI logs, tracking forms and all databases. Participants' names or other individually identifying information will never appear in any report resulting from this project. Separate from research records, an identifier key will be created to link the PIN to participant names and contact information in order to facilitate follow-up with participants and enter in data collected through record review (i.e., biologic functioning and clinic attendance). This identifier key will be stored separately from any research data or research-related forms (e.g. informed consent forms). All research data, research-related forms, and the identifier key will be secured in a locked cabinet or a password protected, encrypted laptop in a locked room. Electronic data will be routinely backed up onto an encrypted external hard drive. Encrypted data will be transferred via encrypted files to the co-PI ([name]) for quality control. Only essential project staff will have access to project data. To track participants, PI, co-PIs, and Project Coordinator will have access to a password-protected master file list linking PINs to patient records, kept in an encrypted laptop under lock and key. Electronic data will have several protections: (1) data will be securely transferred with an encrypted cloud-hosted platform (OneDrive) from Ghana to Rhode Island Hospital's data-encrypted

servers; (2) all study staff will be trained in participant data confidentiality protocols and will be consistently monitored by the co-PI on data safety and confidentiality; (3) audio files generated from the qualitative interviews will be designated with a code to ensure name confidentiality and delivered securely to a HIPAA-compliant transcription service.

Data sent and received via text messages to participants' phones for our intervention's open trial (Aim 1) and pilot (Aim 2) will be stored on a cloud-hosted server established by our technology provider (Dimagi). Text message content will not contain any identifying information or direct references to HIV, HIV treatment, or the HIV clinic. At participants' request, text messages can also be password protected. Three pieces information linked to PINs will be stored on the server for participants in these two phases of the study: (1) participants' phone numbers, (2) biologic functioning (CD4+ count, viral load), and (3) clinic appointments. For this reason, we will use Dimagi's HIPAA-compliant software to encrypt, back up, and securely store this participant data. Study staff will have full access to the server in order to upload data and monitor system use through a secure, password-protected internet portal. YPLH participants will also have partial access to the server with a password-protected user-friendly web interface which allows them to view their own personal information but not others' information. YPLH participants will also be able to view a leaderboard consisting of the anonymized names of other participants and their game point totals, as part of the Text-Based Adherence Game intervention. For example, they may see that Player X is in first place with 75 points and Player Y is in second place with 54 points. Participants will NOT be able to view each other's phones number, biologic functioning, or clinic appointments in order to protect privacy. Passwords for access will be changed periodically to ensure the security of these data.

To ensure data quality of qualitative data, digital recordings of the qualitative interviews and youth advisory board meetings will reviewed within 48 hours of the interview by the co-PI. Additionally, after the data is transcribed, transcripts will be checked for accuracy against the data files.

Potential Risks

There are potential risks for participants in this study: (1) potential coercion, (2) emotional discomfort from discussing sensitive topics, and (3) confidentiality breaches.

Protection Against Risk

1. Potential Coercion. The risk of potential coercion to participate will be minimized by following standard procedures for obtaining the informed consent from participants. Study personnel will fully explain the study procedures, risks, benefits, and alternatives to participants. Participants will also be reminded that study participation is voluntary and that refusing to participate or withdrawing from the study at any time will not result in any negative consequences. Recruitment for both phases of the project (Development Phase and Randomized Pilot Phase) will involve the same screening procedures.

2. Emotional discomfort. Discussing sensitive topics such as HIV infection and sexual behaviour may cause psychological distress. Study staff will continually monitor the participant for signs of distress during interviews, assessments, and introductions to the text message intervention. If signs of distress are apparent, the interviewer will offer to pause the session until the participant feels well enough to carry on and also offer more counselling and support. The participant will also be reminded that they may stop the session or un-enrol from the study at any time without penalty. In addition, the Co-PI is a US-based licensed clinical psychologist, who, while working through the PI and Project Coordinator (if not on site himself), will offer clinical advice for participants experiencing emotional distress or in need of psychological and/or psychiatric care. Participants in need of psychological or psychiatric help will be given a referral to these services.

3. Breach of confidentiality. During the consent process, risks of breaches in confidentiality will be highlighted including legal norms that would require a break in confidentiality. Research staff will receive training on the importance of keeping participant information confidential through proper record-keeping. No participant information including name, phone number, and health records will be shared with other participants in the open trial and randomized pilot through the Text-Based Adherence Game. No text messages received as part of this intervention will include this information either. Participants in the youth advisory group will also be informed

during the consent process that, while the rules of participating in the group include keeping other group member's participation in the group private, this cannot be guaranteed.

Medical or Professional Intervention in Event of Adverse Event. Although we do not anticipate any events in need of medical intervention associated with our study activities, due to our sample of YPLH we do recognize the need for some safeguards. All participants will be under the care of a physician as our study site is based in a public hospital HIV clinic and prescription of ART is an eligibility criteria of our study. All adverse events will be immediately reported to the PI. Serious adverse events will be reported to the KATH IRB, the KNUST IRB, and Rhode Island Hospital IRB as stipulated by the regulations of the IRB.

Potential Benefits of the Proposed Research to Participants and Others

There may be little or no direct benefit to participants from this study as this study is developing a novel text message program that may or may not improve adherence to HIV care for patient participants. However, reports from previous research have indicated that many participants feel that sharing information about their experiences of living with HIV or receiving HIV treatment with trained staff can be therapeutic. If requested, YPLH participants will be given information on HIV treatment, as well as referrals to local health and social services. Referrals to more intensive resources will be made as needed.

Importance of Knowledge to be Gained

This study will fill key gaps in scientific knowledge about the barriers and facilitators to HIV treatment adherence among YPLH in sub-Saharan Africa. Background literature suggests that this group has high rates of ART nonadherence, treatment attrition, and viral nonsuppression, and that these outcomes may be associated with the developmental transition from adolescence to adulthood. Additionally, the literature identifies key factors that influence ART adherence at the individual-, social-, and contextual-levels which can possibly be targeted through an engaging intervention using novel technology-based strategies. Thus, the risks of the proposed study are reasonable and balanced by the potential contribution of providing important information that can advance our knowledge of adherence to HIV care among

YPLH and whether the proposed intervention will improve adherence outcomes during this unique and vulnerable period of life.

Data and Safety Monitoring Plan

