become invested in the patient's well-being which creates a closer, more supportive relationship. Alternatively, the friend may see this task as a burden and the relationship suffers. Our modified SAT model predicts that by (a) increasing YPLH's personal capabilities related to adherence (skills, knowledge, and beliefs), (b) providing greater access to clinic and peer adherence social support, and (c) positively altering their relationship and interactions (social interdependence) with an identified supportive person, problems with developmental transitions are overcome and adherence behavior is improved. In addition, while many individual and sociostructural contextual barriers to adherence such as emotional problems and access to transportation cannot fully be addressed with a Text-Based Adherence Game, mobile access to clinic staff who can provide referrals for services can help YPLH better overcome these barriers. Finally, the model suggests that when YPLH receive feedback on their HIV-related health outcomes, their motivation to engage in protective health behaviors is enhanced.

METHODOLOGY

This research will be divided into two phases: (1) a Development Phase (Aim 1: *Develop*) in which we will conduct formative research to guide development of a Text-Based Adherence Game and gain experience with its implementation in an iterative open trial and (2) a Randomized Controlled Pilot Phase (Aim 2; *Evaluate*). See Table 1 for Study Timeline.

Table 1: Study Timeline

Quarters	Year 1				Year 2				Year 3				Year 4			
	1	2	3	4	1	2	3	4	1	2	3	4	1	2	3	4
Aim 1: Develop																
Game/system creation	•	•	•													
Iterative trial			•	•	•											
Aim 2: Evaluate																
Recruitment			•	•	•											
Randomized pilot			•	•	•	•	•	•	•	•	•	•				
Analyses					•	•	•	•	•	•	•	•				

Inclusion criteria. Inclusion criteria for YPLH: Males and females living with HIV, 18 to 24 years old, will be eligible for enrollment in each phase of the study according to the following criteria: (1) read English *and* speak English or a local language spoken by clinic staff (e.g., Twi), (2) in medical care for HIV and receiving ART at our clinic, (3) aware of their HIV status as per clinical record, (4) not impaired by

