cognitive or medical limitations per clinician report, (5) possess a cellphone, and (6) able to give consent. *Adolescents living with HIV (ALH) between the ages 12-17 will also be eligible to participate in focus groups and cognitive interviews as part of a separate component of the Development Phase. Their eligibility criteria is as follows:* (1) *read English and speak English or a local language spoken by clinic staff (e.g., Twi),* (2) *in medical care for HIV and receiving ART at our clinic,* (3) *aware of their HIV status as per parent/guardian report,* (4) *not impaired by cognitive or medical limitations per clinician report,* (6) *able to give assent, and* (7) *their parent/guardian is able to give consent. Parents or guardians of ALH are also able to participate in focus groups and cognitive interviews as part of this separate component. Parent eligibility is as follows:* (1) *speak English or a local language spoken by clinic staff (e.g., Twi),* (2) *own a mobile phone,* (3) *aware of their child's HIV status,* (4) *not impaired by cognitive or medical limitations per clinician report, and* (6) *able to give consent.* Participants in the randomized pilot must have also demonstrated a recent detectable viral load. Study staff will NOT make changes to ART regimens and participants will be encouraged to speak with their doctor if they have concerns about their medications or side effects of these medications. Any unexpected ethical issues that arise with our participants will be discussed immediately with the PI. All participants will receive a resource packet including information on ART as well as references to local health and social services. We will also encourage participants to identify a treatment monitor to take part in the game. This will not be a requirement for our study, however, because those who begin playing the game without a monitor will be incentivized via game rewards to recruit one (and we will assess this occurrence). Participants without a monitor will be assigned a peer educator to fill this role. Inclusion criteria for treatment monitors includes: 1) *read English and speak English or a local language spoken by clinic staff,* (2) *target HIV patient has agreed to their participation,* (3) *aware of target patient's HIV status as per patient report,* (5) *possess a cellphone, and* (6) *able to give consent.*

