Identifying eligible patients and consent procedures. Eligible patients will be identified by clinic and research staff involved with the project. All eligible YPLH will be recruited consecutively until our desired sample size is obtained. Research staff including the Research Assistant and Project Coordinator will conduct the informed consent in a private clinic room.

Development Phase (Aim 1)

The goal of the Development Phase is to create our Text-Based Adherence Game using a two-step approach: youth advisory board meetings followed by an iterative open

trial. The youth advisory board will be made up of five to eight YPLH. Findings from each step of this phase will be presented at board meetings held three to five times. Audio from board meetings will be digitally recorded. A working group will also be established consisting of the Project Coordinator, a clinic staff member, and the PI and Co-PI's. The working group will meet regularly for the entire project to oversee study implementation.

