Adolescent and parent component. The Development Phase will also consist of a separate three-step component to explore the creation of a version of our Text-Based Adherence Game for ALH and their parents. First, 12-16 ALH will be recruited to participate in one of three focus groups. One group will include younger adolescents (12-14 years-old), one will include older adolescents (15-17 years-old), and one will have adolescents of all ages. An approximately equal number of male and female adolescents will be recruited. The same number of parents (or guardians) of ALH will participate in their own focus groups. Each group will have 4-6 participants. Groups will be led in English or a local language, preference given to participants, by trained facilitators following a semi-structured focus group protocol, be conducted in private spaces at the Clinic, and last approximately two hours. ALH and parents will each be given 40 cedis for their participation. Parent and adolescent protocols will mirror each other and assess (1) barriers and facilitators to adolescent HIV treatment adherence with a focus on parenting practices and family relationships and (2) preferences for the Text-Based Adherence Game. Groups will be audio-recorded, translated (if necessary), and transcribed. Second, information gained from focus group data will be used to create a parent-based version of the Text-Based Adherence Game (see Game and system development below) to fit the needs and preferences of ALH and their parents. Third, 10 parent-adolescent dyads will participate in one of three rounds of cognitive interviews to evaluate usability of intervention prototypes. After each round of interviews, changes will be made to the intervention based on participant feedback. Cognitive interviews will be led in English or a local language, preference given to participants, by a trained facilitator in a private Clinic space and last approximately one hour. ALH and their parents will be interviewed separately and together. Interviews will be audio- recorded, translated (if necessary), and transcribed. ALH and their parents will each be given 40 cedis for their participation. Focus group and

cognitive interview parent participants will also complete a brief demographic and child health survey.

[figure not shown]

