A Text-Based Adherence Game for Young People Living with HIV in Ghana

Contents

- A. Draft of Focus Group Guide: Adolescent Patient
- B. Draft of Focus Group Guide: Parent/Guardian of Adolescent
- C. Draft of Cognitive Interview Guide: Parent-Adolescent Dyad

A. Focus Group Guide: Adolescent Patient

The investigators will lead a semi-structured focus group with adolescent patient participants to gather information that will provide guidance in developing a Text-Based Adherence Game intervention. Following the Introduction outline below is an outline for the Focus Group. Each focus group topic is followed by broad and generally open-ended questions. Interviewers will be instructed to ask more specific follow-up questions to probe responses to the initial open-ended questions. **While this guide provides the main topics of interest, initial questions, probes, and ordering of topic areas may be modified prior to the start of the focus group and during the focus group.**

Introductions

Overview: The intent of this portion of the agenda is to welcome the participants and make them as comfortable as possible by explaining the interview process and letting them know what to expect from the experience. Additionally, the investigator will explain rules concerning confidentiality, and the use of data.

- Introduce Investigator
- Explain that the overall purpose of focus group is to elicit discussion about the participant's experiences with HIV, HIV treatment, and technology, and their preferences for text message intervention to improve their HIV treatment adherence.
- Sample dialogue: *"Thank you so much for agreeing to be a part of this focus group. We are here today to learn about you and find out how young people feel about living with HIV and getting treatment for HIV. In addition, we're curious to find out about your experience with mobile technology including cellphones, text messages, the internet, and mobile games. Our idea is to create a game that is played through text messages. The game will be fun and help young people connect with their parents or other supportive people in their life and focus on their HIV treatment. We want to know what people think about this idea. You are the expert in this area and we are hoping that you will share your thoughts about these topics. We really need to learn from you in order to make this program successful."*
- Housekeeping: rest rooms, refreshments, breaks

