- Ground rules: *"You do not have to answer any questions you are uncomfortable with. There is no right or wrong answers. We're interested in all opinions."*
- Confidentiality: *"We will work hard to make sure everything said in the interview will not be shared with anyone outside of the research team unless you tell us about a situation where you or someone else is in danger. You are also being asked to not share anything you hear about other focus group members with people outside of this focus group. What gets said in this focus group stays here. We want everyone to feel safe and comfortable to share their experiences."*
- Digital Recording: *"Recordings are not shared with anyone outside of the research team, they are kept safe and private. When information is taken from the recording, participants will be identified by a number only and names will not be used. Tapes will be erased once transcribed."*

Focus Group Outline

Demographic/Family Information: Participants will be asked general questions about their family and friends, living situation, and current schooling.

"I would like to start by getting to know all of you a little bit better."

- "Tell me about yourselves"*
- "Tell me about your families"*
- "What languages do you speak at home?"*
- "What do you like to do in your free time?"*

- “Tell me about your school.”
- “Tell me about your friends.”

Experience of Living with HIV: Participants will be asked preliminary questions about their experience of living with HIV.

“I would like to hear about your experiences with living with HIV.”

- “Tell me about the time when you found out you were HIV positive”
- “What’s your understanding of how you were infected?”
- “How do you feel about it now?”
- “What’s it like being a young person living with HIV?”
- “What do people in your community say about HIV?”
- “Who in your life is aware of your HIV status? Who is not aware?”
- “What’s it like to tell people your status?”

Barriers and Facilitators to HIV Treatment Adherence: Participants will be asked about the barriers and facilitators to treatment adherence.

“I would like to hear from you your experience with HIV treatment.”

- “Tell me what HIV treatment has been like for you.”
- “What makes it hard take antiretroviral (ART) medication?”
- “What makes it easier to take ART medication?”
- “What are the things that make it hard or easy come to medical appointments?”
- “What’s it like taking your medication at boarding school?”

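### Awareness of HIV status in 12-17 year-olds rests on parent/guardian report, with no second check visible before HIV is named to the minor

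*Combined protocol and SAP*

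**What the plan says.** The protocol's Inclusion criteria paragraph (Methodology) sets separate rules for two age groups.

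- Participants aged 18-24 must be "aware of their HIV status as per clinical record".
- For the separate adolescent component, "Adolescents living with HIV (ALH) between the ages 12-17 will also be eligible to participate in focus groups and cognitive interviews". Their criterion (3) is "aware of their HIV status as per parent/guardian report". Criterion (4), on cognitive or medical limitations, relies on clinician report. Criteria (6) and (7) require that the adolescent is "able to give assent" and that a parent or guardian can consent.

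Under Adolescent and parent component, the plan states: "First, 12-16 ALH will be recruited to participate in one of three focus groups". Ten parent-adolescent dyads then take part in cognitive interviews. On screening, the plan says only that "Eligible patients will be identified by clinic and research staff involved with the project".

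The adolescent focus group guide tells members that the aim is to "find out how young people feel about living with HIV and getting treatment for HIV". It later prompts: "Tell me about the time when you found out you were HIV positive". The cognitive interview guide refers to the young person's HIV treatment in its introduction and in its joint questions.

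**The concern.** An awareness criterion is needed only if some adolescents at the clinic may not know their diagnosis. The parent focus group guide points the same way: it asks when the child became aware, and what the child does and does not know about HIV. A parent may be mistaken, or may count a partial explanation as full awareness.

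If that happens, study staff could be the ones who reveal the diagnosis to a child, and this cannot be undone. The distress procedures under Protection Against Risk (monitoring, pausing, referral) come into play only once distress is apparent. The issue is protection of minors, not inference.

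**Working it through.** There is no figure in the plan to reproduce. The check sets the relevant sections side by side.

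1. **Source of the awareness criterion.** Ages 18-24: clinical record. Ages 12-17: parent/guardian report. No reason is given for the difference, and no second source is named for the younger group.

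2. **Clinic input elsewhere in adolescent screening.** Criterion (4) already needs a clinician's report on each adolescent. A clinic source is therefore in use for the criterion next to awareness, but not for awareness itself.

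3. **Other steps that might act as a check.**
   - Identifying eligible patients and consent procedures: clinic and research staff find candidates, but no awareness check is described.
   - Parent eligibility: the parent must know the child's status. That concerns the parent's knowledge, not the child's.
   - Assent: required, but its script is not in the text reviewed. Assent to an HIV adherence study may itself name HIV, so it can be the point of disclosure as well as the point at which an error surfaces.

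4. **Points at which HIV is named.** First, possibly, the invitation or assent. Then the focus group, where the introduction names HIV and the questions presuppose that members know. Then the cognitive interview, which enters under the same criterion.

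5. **Risk section.** Potential Risks lists coercion, emotional discomfort and confidentiality breaches. Unintended disclosure of the diagnosis to an adolescent is not listed.

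6. **Number of adolescents covered.** Focus groups: 12-16. Dyads: 10. If no one takes part in both, 12 + 10 = 22 to 16 + 10 = 26. If all dyad adolescents also attend a group, 12-16. The documents do not say which applies.

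7. **Where confirmation could come from.** The chart abstraction form in Appendix 2 has 25 items. It records HIV status at presentation and route of infection, but has no field for what the patient knows. A chart look-up alone may therefore not answer the question, whereas a clinician's report can.

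**The case against.** The best defence is that a parent may know better than a chart what a child has been told. The parent guide treats parents as informants on exactly this, and the documents do not rank the two sources. Calling parent report weaker is a judgement. This stands, and it is a reason to keep parent report and add to it rather than replace it.

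A second defence is the missing text. Consent and assent pages, and some other sections, were not in the copy reviewed, and an awareness check could sit there. This also stands; the point is limited to what can be seen.

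Three stronger readings are tempting but not supported:

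- **That a child would learn the diagnosis in front of peers.** Assent comes first, and the consent section places informed consent in a private clinic room. A wrong report would more probably surface there. The focus group is a fallback route: its guide is a draft, its questions may be changed, and answering is optional.
- **That the risk can be given as a percentage.** With an assumed error rate q per parent report, 1 - (1 - q)^n for n = 12 to 16 focus group members gives about 11-15% at q = 1%, 22-28% at 2% and 46-56% at 5%. No document supports any of these rates, and the formula assumes independent errors and that assent catches no one. Adding the 10 dyads raises the figures but brings in adolescents who are not in that setting.
- **That other group members would be exposed, or the component halted.** All members are adolescents living with HIV and are asked to keep what they hear private. Nothing in the documents supports either consequence.

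**Conclusion.** The point holds as a cheap improvement to participant safety. Adolescents are accepted as aware on parent/guardian report, the available text names no confirmation before HIV is mentioned to them, and the session guides presuppose awareness. Unintended disclosure is possible, most plausibly at assent and otherwise in a focus group or cognitive interview.

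The size of the risk cannot be estimated from the documents; only the number of adolescents covered can be stated (12 to 26). The conclusion assumes that the text not available for review contains no awareness check. It does not bear on the outcomes, sample size or analysis of the randomized pilot, which enrols only 18-24 year-olds.

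**What to change.** Reword adolescent criterion (3) along these lines: aware of their HIV status as per parent/guardian report, confirmed by clinician report (or by the clinical record where disclosure is recorded). Obtain the confirmation together with the clinician report already required for criterion (4), and state that it must be complete before any invitation or assent material reaches the adolescent. If the consent or assent documents already contain such a check, a cross-reference in the criterion is enough.

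The cost is one eligibility line and one further question to a clinician who is already reporting on the adolescent. The downside is that some adolescents whose awareness the clinic cannot confirm will not be approached. How many is unknown, and relying on charts alone could make the number larger because disclosure to minors may not be recorded.
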